2.1. IL-5 Antagonists

Two monoclonal antibodies (mepolizumab and reslizumab) that bind IL-5 and block its interaction with IL-5R were approved to reduce asthma exacerbations beyond corticosteroids or β_2 -adrenergic bronchodilators alone. IL5 promotes eosinophil recruitment, survival and degranulation, leading to airway inflammation and increasing asthma exacerbation incidences. The anti-IL-5 antibodies inhibits IL-5 activity, leading to a reduction in circulating eosinophils and their associated granule proteins, including eosinophil cationic protein (ECP) and eosinophil-derived neurotoxin (EDN).

These drugs were approved after demonstrating a reduction of asthma exacerbations in patients with eosinophilia. In these patients, increased blood eosinophils and their activation drive poor lung function. Therefore, the reduction of asthma symptoms after treating with mepolizumab or reslizumab is associated with an accompanying decrease in circulating eosinophils, identifying peripheral blood eosinophils as the primary PD biomarker. In addition to assessing blood eosinophils and its PD parameters (e.g. area under the effect curve and time of maximal response) at single dose levels, we will also explore modeling-based approaches (e.g., E_{max} , EC_{50} , and slope of concentration-effect relationship) to the PD data.

2.2. Summary

This study will obtain data over a range of doses, including information on the steep part of dose-/exposure-response curve, to inform clinical trial operating characteristics of subsequent PK and PD similarity studies for these drugs. This would be similar to and could substitute for what is suggested as a pilot study in the existing FDA biosimilars guidance. The study will collect data on various PD markers to better understand the dose-response relationship and variability in healthy subjects of traditional PD measurement-based approaches at a single dose (e.g. AUEC and maximal response at a single time point). The study will also evaluate use of model-based approaches for analyzing data from the various dose levels to inform dose selection for similarity studies. In addition, as many biologics from other classes do not have biomarkers associated with the known mechanism-of-action, this study will explore the use of proteomics and small RNA transcriptomics, and the analytical approach needed to identify and characterize circulating biomarkers that could be used for a PD similarity assessment.

3. Study Objectives

3.1. Primary Objective

The primary objective of this study is:

1. To inform clinical trial operating characteristics for future clinical pharmacology PK and PD similarity studies using the different biomarker-based approaches.

3.2. Secondary Objectives

The secondary objectives of this study are:

1. To determine the values and variability of PK and PD characteristics at four dose levels (i.e., low, intermediate low, intermediate high, and high doses).
2. Explore PK and PD relationships using appropriate models

3.3. Exploratory Objective

The exploratory objective of this study is:

1. To evaluate the utility of circulating proteins and small RNAs as potential PD biomarkers.
2. To inform on the analytical approach and experimental design needed for identifying exploratory proteomic- and RNA-based PD biomarkers in plasma

4. Study Endpoints

4.1. Primary Endpoints

The primary endpoint of this study is:

1. The values and variability of standard PD metrics (AUEC and maximal difference at a single time-point) for eosinophils at low, intermediate low, intermediate high, and high doses of mepolizumab and reslizumab.

4.2. Secondary Endpoints

The secondary endpoints of this study are:

1. The values and variability of pharmacokinetic characteristics (C_{max} and AUC of free drug concentration) at low, intermediate low, intermediate high, and high doses of mepolizumab and reslizumab.
2. Parameters (E_{max} , and EC_{50}) calculated by the model after combining data from low, intermediate low, intermediate high, and high doses of mepolizumab or reslizumab with placebo data.

4.3. Exploratory Endpoints

The exploratory endpoint of the study is:

1. Plasma proteomics (differential expression of circulating proteins)
2. Plasma small RNA transcriptomics (differential expression of circulating small RNAs)

5. Investigational Plan

5.1. Study Design

This is a pilot, randomized, placebo-controlled, single-dose, parallel arm study. Healthy subjects will be randomized to four dose groups (low, intermediate low, intermediate high, and high) of each drug (mepolizumab or reslizumab) or placebo (see Table 5-1).

Subjects will report to the study site for screening assessments from days -21 to -2 and then will return to the site on day -1 for baseline assessments. Prior to and following

study drug or placebo administration on day 1, they will undergo assessments as described in the Schedule of Events (Table 9-1). Subjects will stay in house for the first two weeks and will return to the clinic for study procedures as identified in the Schedule of Events (Table 9-1).

Depending on the treatment arm, subjects will return to the clinic up to 9 times for PK and PD blood draws and additional study procedures as outlined in the Schedule of Events (Table 9-1).

All subjects will be sampled daily for the first two weeks and then weekly out to Day 63. Subjects in Groups C, D, G, H, and I will be sampled monthly until Study Day 123. Subjects in Groups A, B, E, and F will follow the Schedule of Events until Day 63 and all other subjects will follow the Schedule of Events until Day 123. Each treatment group should include equal representation of male and female subjects.

Table 5-1: Study Treatment Groups

Subjects (n)	Treatment Group	Drug
8	A	Mepolizumab low (3 mg)
8	B	Mepolizumab low intermediate (6 mg)
8	C	Mepolizumab high intermediate (12 mg)
8	D	Mepolizumab high (24 mg)
8	E	Reslizumab low (0.1 mg/kg)
8	F	Reslizumab low intermediate (0.2 mg/kg)
8	G	Reslizumab high intermediate (0.4 mg/kg)
8	H	Reslizumab high (0.8 mg/kg)
8	I	Placebo

5.1.1 Common Procedures

At the study clinic (Spaulding Clinical Research unit in West Bend, Wisconsin), subjects will be screened for study eligibility from Day -21 to Day -2. On Day-1, subjects will enter the study clinic for check-in procedures the day before study drug administration. During the screening visit, the inclusion and exclusion criteria will be reviewed to ensure the subject is appropriate for the study. The informed consent form will be reviewed with the subject by a member of the study team and the subject will be encouraged to ask questions to ensure the subject has a good understanding of the study. If the subject is eligible and agrees to participate, the subject will be asked to sign the informed consent form before any study-specific procedure is performed, including randomization.

After the consent process is complete, demographic data, medical history, and concomitant medications (including over-the-counter and complimentary/alternative supplements) will be recorded. A physical examination will be performed by a study

team member. Clinical laboratory tests (hematology, serum chemistry, and urinalysis) will be performed. Female subjects must have a negative pregnancy test result. Any values outside the reference range will be evaluated for clinical significance. If a value is determined to be clinically significant or the subject has a positive pregnancy test result, the subject will be instructed to follow-up with his or her personal physician. Screening tests will be performed within 21 days of and no later than 1 day before Day-1.

Screening procedures will be performed by clinic staff, and all screening results will be evaluated by the study clinician/investigator against the inclusion/exclusion criteria to confirm subject eligibility. At check-in, eligibility criteria will be reviewed, any changes in medical history (including concomitant medications) will be documented, vital sign measurements and a 12-lead ECG will be performed, clinical laboratory, drug and alcohol, and pregnancy tests (for females) will be performed, an intravenous (IV) catheter may be inserted into the subject's forearm region for blood collection (if needed), study drug will be administered, and blood samples will be collected per protocol.

The FDA project biostatistician will prepare the randomization schedule, and subjects will be randomly assigned to 1 of 9 treatment groups, described in Table 5-1.

Subjects will enter the study clinic for check-in procedures the day before study drug administration of the first period (Day -1). Mepolizumab will be administered subcutaneously (SC) and reslizumab will be administered intravenously; placebo will be administered either subcutaneously or intravenously (4 subjects each). On Day 1, subjects will receive their assigned treatment according to the randomization schedule.

5.1.2 Dosing Schedule

- Treatment Group A: Mepolizumab 3 mg, SC
- Treatment Group B: Mepolizumab 6 mg, SC
- Treatment Group C: Mepolizumab 12 mg, SC
- Treatment Group D: Mepolizumab 24 mg, SC
- Treatment Group E: Reslizumab 0.1 mg/kg, IV
- Treatment Group F: Reslizumab 0.2 mg/kg, IV
- Treatment Group G: Reslizumab 0.4 mg/kg, IV
- Treatment Group H: Reslizumab 0.8 mg/kg, IV
- Treatment Group I: Placebo, (4 subjects receive SC and 4 subjects receive IV)

Subjects in Groups A, B, E, and F will be discharged on Day 63, while all other subjects will be discharged on Day 123. If a subject discontinues from the study prematurely, all procedures scheduled for discharge Day (i.e., Day 63 or Day 123) will be performed.

Meal timing and components, activity levels, and general conditions in the study clinic will be as similar as possible on the treatment days.

Safety will be evaluated in terms of AEs, clinical laboratory results (hematology, serum chemistry, and urinalysis), vital sign measurements (blood pressure, heart rate, respiratory rate, and oral body temperature), safety 12-lead ECG results, and physical examination findings (see Table 9-1).

5.1.3 Risk/Benefit

Subjects will be informed that participation in a human PK-PD study like the present one cannot be of benefit to healthy volunteers. Nevertheless, the information from the physical examination, vital sign measurements, and ECG results may be shared with the subject's personal physician if this is the subject's choice. Subjects will be informed that it is also their choice to inform their personal physician that they are participating in this research study.

Subjects will be informed that their contribution to the study is of major importance to agencies like the U.S. FDA for helping this agency better evaluate biomarkers. However, since this is a study involving healthy volunteers, subjects will be informed that they have the alternative not to participate.

Subjects will be informed that they may be exposed to risks associated with the pharmacological properties of the investigational product and the study procedures. The following summary of potential AEs for the study drugs will be provided to and discussed with the subjects:

1. Mepolizumab (1)

- Hypersensitivity Reactions: Angioedema, bronchospasm, hypotension, urticaria, and rash have occurred in some subjects receiving mepolizumab. Although the majority of these reactions occurred within hours of drug administration, some instances can have a delayed onset over days.
- Opportunistic Infections: In previous controlled clinical trials, two serious adverse reactions of herpes zoster occurred in subjects receiving mepolizumab.
- Adverse Reactions: The most common adverse reactions include headache, injection site reaction, back pain, and fatigue (incidence $\geq 5\%$).

2. Reslizumab (2)

- Hypersensitivity Reaction: Anaphylaxis occurred with reslizumab infusion in 0.3% of subjects in placebo-controlled trials, although only after the second dose.

- **Malignancy:** In previous placebo-controlled clinical trials, 0.6% subjects receiving 3 mg/kg reslizumab had one or more malignant neoplasm reported. The observed malignancies were diverse and were found in different types of tissue.
- **Adverse Reactions:** The most common adverse reaction is oropharyngeal pain (incidence $\geq 2\%$).

The study drugs will not be administered to anyone who is pregnant. All women must take a pregnancy test before receiving any study drug in this study. All woman of childbearing potential enrolled on this study will be informed that they must use effective birth control methods (abstinence, intrauterine device, or contraceptive foam and a condom [i.e., double-barrier method]) during treatment. Subjects will be informed that they must notify the investigator if they or their female partners become pregnant during the study.

Subjects will be informed that insertion of an IV catheter may be required for blood sample collection and, during insertion of the catheter, soreness, bruising, or infection at the insertion site are possible but unlikely. Subjects will also be informed that dizziness and lightheadedness may occur during direct venipuncture, insertion of the IV catheter, or during blood collection.

Subjects will be informed that they may eat only meals and snacks that are provided during periods of their stay in the study clinic, and that they must consume each meal that is served at a reasonable pace (within 25 minutes).

Subjects will be informed that blood samples will be collected for genomics analysis to explore how a person's genes or genome may affect the way the body and drug interact.

Subjects will be informed that the confidentiality of their data will be respected at all times according to state law, and the study personnel handling their study data are bound by confidentiality agreements.

Subjects will be informed that extra precautions will be put in place that will limit the risk of COVID-19. Precautions will be documented in a COVID-19 risk management plan. Currently, this includes phone screening to prevent symptomatic participants from entering the clinic; triage of all potential study subjects entering the building at screening and check-in for potential contacts with COVID-19, signs and symptoms, temperature monitoring and potential serology screening for severe acute respiratory syndrome corona virus 2 (SARS CoV-2); SARS CoV-2 molecular testing just prior to or at check-in for admission to the study floor; all study participants and staff wearing masks except when in in their beds with a curtain drawn between subjects or for a limited time for a study procedure (e.g. study drug administration); staff wearing personal protective equipment, social distancing during screening and in-house stays including 2 subjects per room for overnight stays; extra hand sanitation stations with hand washing and sanitation policies

per CDC recommendations; closing common areas and serving food at subjects' room resulting in subjects spending most of their time in their rooms with the exception of specified times for walking in the halls; daily temperature screening; and separate staff for confined vs. not-confined participants whenever possible. Designated isolation rooms will be set up to segregate any participant(s) that develop any symptoms of concern while housed in the unit and COVID-19 testing will be done when deemed necessary by the Investigator. Subjects will be informed that despite the extra precautions there is still a risk of them contracting COVID-19. Any changes to the COVID-19 precautions (e.g. due to updated CDC recommendations or new testing becoming available) will be documented in the COVID-19 risk mitigation plan.

Subjects will be informed that the study drug and all tests, procedures, and visits required by the study are provided at no cost to them. If subjects become ill or physically injured because of participation in this study, they will be informed that costs of treatment will not be covered by the sponsor.

If a subject becomes pregnant, she will be informed that neither Spaulding Clinical Research nor the FDA will be responsible for the cost of any obstetric or related care, or for the child's care.

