5.2.1 Inclusion Criteria

Subjects who meet all the following inclusion criteria will be eligible to participate in the study:

1. Subject signs an IRB approved written informed consent and privacy language as per national regulations (e.g., Health Insurance Portability and Accountability Act authorization) before any study related procedures are performed.
2. Subject is a healthy man or woman, 18 to 55 years of age, inclusive, who has a body mass index of 18.5 to 29.9 kg/m², inclusive, at Screening.
3. Subject has normal medical history findings, clinical laboratory results, vital sign measurements, 12 lead electrocardiogram (ECG) results, and physical examination findings at Screening or, if abnormal, the abnormality is not considered clinically significant (as determined and documented by the investigator or designee).

4. Subject must have a negative test result for alcohol and drugs of abuse at screening and Check-in (Day -1).
5. Subject has a peripheral blood eosinophil count of ≥ 50 and ≤ 700 cells per microliter as measured by a standard hematology analyzer.
6. Female subjects must be of non-childbearing potential or, if they are of childbearing potential, they must: 1) have been strictly abstinent for 1 month before Check-in (Day -1) and agree to remain strictly abstinent for the duration of the study and for at least 1 month after the last application of study drug; OR 2) be practicing 2 highly effective methods of birth control (as determined by the investigator or designee; one of the methods must be a barrier technique) from at least 1 month before Check-in (Day -1) until at least 1 month after the end of the study.
7. Male subjects must agree to practice 1 highly effective method of birth control (as determined by the investigator or designee) from at least 1 month before Check-in (Day -1) until at least 1 month after the end of the study.
8. Subject is highly likely (as determined by the investigator) to comply with the protocol defined procedures and to complete the study.

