5.6.3.2 Treatment

The following procedures and assessments will be performed during the treatment period according to the Schedules of Events (Table 9-1):

- Record concomitant medications
- Monitor for AEs
- Perform clinical laboratory tests
- Administer study drug according to the randomization schedule following all other pre-dose examinations and specimen collection
- Perform a complete or targeted physical examination
- Measure vital signs (blood pressure, heart rate, respiratory rate, and oral body temperature). If vital signs are scheduled at the same time as another event, vital signs will be measured after the ECG, but before blood sample collection
- Perform safety 12-lead or telemetered ECG monitoring. If scheduled for the same time, safety 12-lead or telemetered ECG monitoring will always be performed before vital sign measurement and blood sample collection
- Perform alcohol and drug screening (amphetamines, barbiturates, benzodiazepines, cannabinoids, cocaine, alcohol, opiates, phencyclidine, propoxyphene, and methadone)
- Collect urine sample (3-5 mL) for omic analyses (e.g., metabolomics)
- Collect PK blood samples (5 mL). There are no washout periods for this study

- Collect blood eosinophil blood samples (3.5 mL) for flow cytometry
- Collect whole blood (5 mL) for plasma proteomic and small RNA transcriptomic analyses
- Collect buffy coat for genomic analyses

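### Protocol Section 5.1.3 gives women of childbearing potential a contraception instruction that conflicts with inclusion criterion 6 on method and on duration

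*Protocol*

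**What the plan says.** Section 5.1.3 of the protocol (Risk/Benefit) lists what subjects will be told. Enrolled women of childbearing potential will be informed that they "must use effective birth control methods (abstinence, intrauterine device, or contraceptive foam and a condom [i.e., double-barrier method]) during treatment". The sentence does not refer to the eligibility criteria.

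Inclusion criterion 6, in Section 5.2.1 and again in the Synopsis, gives a woman of childbearing potential two routes:

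- **Abstinence.** She has been strictly abstinent for a month before check-in, and must "agree to remain strictly abstinent for the duration of the study" and "for at least 1 month after the last application of study drug".
- **Two methods.** She must "be practicing 2 highly effective methods of birth control", as judged by the investigator or designee, and "one of the methods must be a barrier technique". This applies "from at least 1 month before Check-in (Day -1) until at least 1 month after the end of the study".

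Each subject receives one dose, on Day 1. On the end of participation, Section 5.1.2 says: "Subjects in Groups A, B, E, and F will be discharged on Day 63, while all other subjects will be discharged on Day 123". Section 5.6.3.2 speaks of procedures performed "during the treatment period according to the Schedules of Events", so the protocol does at times use treatment for the period after the dose. The SAP does not address contraception.

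**The concern.** The protocol gives the same women two different rules on a safety matter, and no section says which prevails or that one summarises the other. Criterion 6 is not only an entry check. It commits the woman to conduct through follow-up and, for two-method users, beyond it. Section 5.1.3 then states what she must do once enrolled. A woman who qualified on an intrauterine device plus a barrier could follow Section 5.1.3, drop the barrier, and so break the rule under which she was enrolled.

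The month after discharge deserves most attention. Section 5.1.3 asks subjects to report a pregnancy that occurs during the study, and Section 5.7.4.1.2 ends adverse event recording at discharge or early termination. Neither expressly covers the further month that criterion 6 asks of two-method users.

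**Working it through.** The plan states no figure to reproduce. The check is a comparison of texts plus day arithmetic.

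**Method**

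| Item | Section 5.1.3 | Criterion 6 |
|---|---|---|
| Standard | effective | highly effective (two-method route) |
| Abstinence | accepted | accepted if strict |
| Intrauterine device alone | accepted, because the list is joined by *or* | not accepted: one method, and not a barrier |
| Foam and condom | accepted | depends on the investigator's judgement of highly effective |
| Oral contraceptive plus condom | not on the list | could be accepted, subject to the same judgement |

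The last row matters because the protocol exempts oral contraceptives from its medication ban (Sections 5.2.2 and 5.8.8). If the Section 5.1.3 list is exhaustive, it is looser than criterion 6 in one place and narrower in another. The safety concern is the looser part.

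**Duration**

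Inputs: dose on Day 1; discharge on Day 63 (Groups A, B, E, F) or Day 123 (Groups C, D, G, H, I). Assumptions: a month is 30 days, with 28 to 31 as the range, and the end of the study is the subject's own discharge day.

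End date under criterion 6:

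- Two methods, discharge day + 30: 63 + 30 = Day 93 (range 91 to 94), or 123 + 30 = Day 153 (range 151 to 154).
- Abstinence, the later of discharge and one month after dosing: 1 + 30 = Day 31 (range 29 to 32), which falls before Day 63. The binding date is therefore discharge, Day 63 or Day 123.

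Section 5.1.3 does not define the period of treatment, so both readings are shown:

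| Reading of treatment | Section 5.1.3 ends | Gap, two methods | Gap, abstinence |
|---|---|---|---|
| To discharge | Day 63 or 123 | 93 − 63 = 30 days; 153 − 123 = 30 days | 0 |
| Day 1 dose only | Day 1 | 93 − 1 = 92 days; 153 − 1 = 152 days | 63 − 1 = 62 days; 123 − 1 = 122 days |

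Section 5.1.3 also omits the month before check-in. That month is already past when a woman is enrolled and is checked at entry, so it adds little.

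**Number of women**

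- Planned: 9 × 8 = 72 subjects, and 72 × 0.5 = 36 women (64 × 0.5 = 32 in the active arms, 8 × 0.5 = 4 on placebo).
- With all 14 replacements: 72 + 14 = 86 subjects, and 86 × 0.5 = 43 women.

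The documents do not say how many would be of childbearing potential, or how many would rely on two methods.

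**The case against.** The best defence is that criterion 6 controls. Section 5.2 enrols only subjects who meet every criterion, the criteria are reviewed at screening and check-in (Sections 5.6.2 and 5.6.3.1), and criterion 6 carries its own forward commitment. Section 5.1.3 is risk information and does not claim to replace it. A woman who abstains, or who uses an intrauterine device with a condom, satisfies the method part of both texts. What women are actually told will be in the consent form approved by the institutional review board, which was not available here. Pregnancies on study are covered by notification, withdrawal and follow-up (Sections 5.1.3, 5.5 and 5.7.4.1.5).

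Much of this stands, and it limits the harm. It does not remove the conflict: Section 5.1.3 is worded as an obligation, names specific methods without marking them as examples, and does not point to criterion 6.

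Some stronger readings are tempting, but the documents do not support them:

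- *Ineligible women could be enrolled.* The entry checks just described prevent this inference.
- *Section 5.1.3 is looser throughout.* Read as exhaustive, it also leaves out combinations that criterion 6 could accept.
- *Abstinent women also lose a post-study month.* Criterion 6 does not ask one of them, because a month after the single dose falls well before discharge.
- *At most 36 women are affected.* Replacements can raise exposure to 86 subjects, and the sex split is described as approximate, so neither 36 nor 43 is a strict bound.
- *Women will in fact be told the looser rule at consent.* Without the consent form this is unknown.

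It can also be said that correcting the contraception sentence leaves the limits on pregnancy notification and adverse event recording as they are. That is true. Whether to extend them is a separate decision for the sponsor.

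**Conclusion.** The conflict is real. On method, Section 5.1.3 accepts an intrauterine device by itself and asks for effective rather than highly effective contraception. On duration, the shortfall depends on what treatment means. On the reading most favourable to the plan it is about one month, for two-method users only. On the narrowest reading it is the whole follow-up for abstinent women, and the follow-up plus a month for two-method users. These dates rest on a 30-day month and on each subject's own discharge day as the end of the study.

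Roughly 36 women at the planned size, or 43 at the maximum, would receive the instruction if the sexes were equal and all were of childbearing potential. The real number is not given, and the conflict does not depend on it.

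The point concerns the safety information given to participants. It has no bearing on design, endpoints, sample size or analysis, and its severity is low.

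**What to change.** In Section 5.1.3, replace the bracketed list of methods and the words that limit it to treatment with a direct cross-reference to inclusion criterion 6 in Section 5.2.1, or with that criterion in full: both routes, each with its own start and stop times. Then confirm that the consent form carries the same rule.

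The cost is one sentence in the protocol and a check of the consent form. As a protocol change it needs approval from the local institutional review board (Section 8.3.1). Nothing in the design, sample size or SAP changes.
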